5.6.4 Selection of Doses in the Study

5.6.4.1 Rationale for Dose Selections

The doses of 300 mg GLE and 120 mg PIB were selected to optimize efficacy of the combination while maintaining an acceptable safety profile, and to be consistent with the dose selection for GLE and PIB in the currently on-going AbbVie HCV Phase 3 studies.

5.6.4.2 GLE and PIB Dose and Treatment Duration

GLE/PIB 300 mg/120 mg QD regimens with 8-week and 12-week durations were evaluated in non-cirrhotic subjects in registrational trials. Efficacy of 8-week treatment duration is established for GT1-, GT2- and GT3- infected non-cirrhotic subjects [R&D/16/0144, R&D/15/1230]. Fifty-two non-cirrhotic GTs 4, 5, or 6-infected subjects received 8-weeks of GLE/PIB and no virologic failure was observed. Overall, these results conclude that 8-weeks of GLE/PIB 300 mg/120 mg dose is efficacious for non-cirrhotic GT 1 - 6-infected subjects.

Based on modeling and simulations, assuming no subjects experience non-virologic failures, following 8 weeks of GLE/PIB in treatment-naïve HCV-infected subjects with compensated cirrhosis, the predicted SVR₁₂ rate is approximately 98% for GT1, 2, 4, 5, and 6-infected subjects, and approximately 92% for GT3-infected subjects.

5.6.4.3 Risk of Development of Resistance Mutations During Combination DAA Trials

In subjects treated with a DAA, amino acid substitution(s) in the targeted protein conferring resistance to the DAA can be selected. It is expected that PIB, an NS5A inhibitor, will be able to suppress the appearance of virus containing resistance-associated substitutions in NS3 that confer resistance to GLE, because there should not be any cross-

resistance in substitutions resistant to DAAs targeting different proteins. The converse is expected to be true as well – GLE should be able to suppress the appearance of virus containing NS5A substitutions conferring resistance to PIB. In addition, in vitro resistant colony selection studies in HCV replicon cells containing GT1 – 6 NS5A demonstrated that PIB had a high genetic barrier to resistance – very few colonies were selected, and most of those that were selected contained NS5A substitutions that conferred only modest levels of resistance to PIB. Based on accumulated clinical and in vitro data to date, the risk of development of resistant substitutions during GLE and PIB combination trials is reduced when compared to treatment with first generation protease and NS5A inhibitors. The combination of PIB and GLE achieved high SVR rates with few virologic failures in subjects with HCV GT1 – 6 infection in Phase 2 and 3 studies. These results support the prediction that the risk of development of resistance-associated substitutions with GLE and PIB combination treatment is low.

6.0 Complaints

A Complaint is any written, electronic, or oral communication that alleges deficiencies related to the physical characteristics, identity, quality, purity, potency, durability, reliability, safety, effectiveness, or performance of a product/device after it is released for distribution.

Complaints associated with any component of this investigational product must be reported to the Sponsor (Section [6.2.2](#)). For adverse events, please refer to Sections [6.1](#) through [6.1.7.1](#). For product complaints, please refer to Section [6.2](#).

6.1 Medical Complaints

The investigator will monitor each subject for clinical and laboratory evidence of adverse events on a routine basis throughout the study. The investigator will assess and record any adverse event in detail including the date of onset, event diagnosis (if known) or sign/symptom, severity, time course (end date, ongoing, intermittent), relationship of the adverse event to study drug, and any action(s) taken. For serious adverse events considered as having "no reasonable possibility" of being associated with study drug, the

investigator will provide an "Other" cause of the event. For adverse events to be considered intermittent, the events must be of similar nature and severity. Adverse events, whether in response to a query, observed by site personnel, or reported spontaneously by the subject will be recorded.

All adverse events will be followed to a satisfactory conclusion.

6.1.1 Definitions

6.1.1.1 Adverse Event

An adverse event (AE) is defined as any untoward medical occurrence in a patient or clinical investigation subject administered a pharmaceutical product and which does not necessarily have a causal relationship with this treatment. An adverse event can therefore be any unfavorable and unintended sign (including an abnormal laboratory finding), symptom, or disease temporally associated with the use of a medicinal (investigational) product, whether or not the event is considered causally related to the use of the product.

Such an event can result from use of the drug as stipulated in the protocol or labeling, as well as from accidental or intentional overdose, drug abuse, or drug withdrawal. Any worsening of a pre-existing condition or illness is considered an adverse event.

Worsening in severity of a reported adverse event should be reported as a new adverse event. Laboratory abnormalities and changes in vital signs are considered to be adverse events only if they result in discontinuation from the study, necessitate therapeutic medical intervention, (see Section [6.1.7](#) regarding toxicity management) and/or if the investigator considers them to be adverse events.

An elective surgery/procedure scheduled to occur during a study will not be considered an adverse event if the surgery/procedure is being performed for a pre-existing condition and the surgery/procedure has been pre planned prior to study entry. However, if the pre-existing condition deteriorates unexpectedly during the study (e.g., surgery performed earlier than planned), then the deterioration of the condition for which the elective surgery/procedure is being done will be considered an adverse event.

6.1.1.2 **Serious Adverse Events**

If an adverse event meets any of the following criteria, it is to be reported to AbbVie as a serious adverse event (SAE) within 24 hours of the site being made aware of the serious adverse event.

| | |
|---|--|
| Death of Subject | An event that results in the death of a subject. |
| Life-Threatening | An event that, in the opinion of the investigator, would have resulted in immediate fatality if medical intervention had not been taken. This does not include an event that would have been fatal if it had occurred in a more severe form. |
| Hospitalization or Prolongation of Hospitalization | An event that results in an admission to the hospital for any length of time or prolongs the subject's hospital stay. This does not include an emergency room visit or admission to an outpatient facility. |
| Congenital Anomaly | An anomaly detected at or after birth, or any anomaly that results in fetal loss. |
| Persistent or Significant Disability/Incapacity | An event that results in a condition that substantially interferes with the activities of daily living of a study subject. Disability is not intended to include experiences of relatively minor medical significance such as headache, nausea, vomiting, diarrhea, influenza, and accidental trauma (e.g., sprained ankle). |

| | |
|--|--|
| Important Medical Event Requiring Medical or Surgical Intervention to Prevent Serious Outcome | An important medical event that may not be immediately life-threatening or result in death or hospitalization, but based on medical judgment may jeopardize the subject and may require medical or surgical intervention to prevent any of the outcomes listed above (i.e., death of subject, life-threatening, hospitalization, prolongation of hospitalization, congenital anomaly, or persistent or significant disability/incapacity). Additionally, any elective or spontaneous abortion or stillbirth is considered an important medical event. Examples of such events include allergic bronchospasm requiring intensive treatment in an emergency room or at home, blood dyscrasias or convulsions that do not result in inpatient hospitalization, or the development of drug dependency or drug abuse. |
|--|--|

For serious adverse events with the outcome of death, the date and cause of death will be recorded on the appropriate case report form.

6.1.2 Adverse Event Severity

The investigator will rate the severity of each adverse event according to the National Cancer Institute Common Terminology Criteria for Adverse Events (NCI CTCAE Version 4).

The table of clinical toxicity grades "National Cancer Institute Common Terminology Criteria for Adverse Events, Version 4.03" is available from the Cancer Therapy Evaluation Program (CTEP) website at:

http://evs.nci.nih.gov/ftp1/CTCAE/CTCAE_4.03_2010-06-14_QuickReference_5x7.pdf and is to be used in the grading of adverse events. Below are the general grading categories. However, the investigator should always search NCI CTC AE for a given diagnostic/symptomatic AE term to identify and apply specific grading details for that AE entity.

Grading System for Adverse Events (a semi-colon indicates 'or' within the description of the grade).

| | |
|----------------|---|
| Grade 1 | Mild; asymptomatic or mild symptoms; clinical or diagnostic observations only; intervention not indicated |
| Grade 2 | Moderate; minimal, local or noninvasive intervention indicated; limiting age appropriate instrumental ADL* |
| Grade 3 | Severe or medically significant but not life-threatening; hospitalization or prolongation of hospitalization indicated; disabling; limiting self-care ADL** |
| Grade 4 | Life-threatening consequences; urgent intervention indicated |
| Grade 5 | Death related to AE |

ADL = Activities of Daily Living

* Instrumental ADL refer to preparing meals, shopping for groceries or clothes, using the telephone, managing money, etc.

** Self-care ADL refer to bathing, dressing and undressing, feeding self, using the toilet, taking medications, and not bedridden.

6.1.3 Relationship to Study Drug

The investigator will use the following definitions to assess the relationship of the adverse event to the use of study drug:

Reasonable Possibility After consideration of factors including timing of the event, biologic plausibility, clinical judgment, and potential alternative causes, there is **sufficient** evidence (information) to suggest a causal relationship.

No Reasonable Possibility After consideration of factors including timing of the event, biologic plausibility, clinical judgment, and potential alternative causes, there is **insufficient** evidence (information) to suggest a causal relationship.

For causality assessments, events assessed as having a reasonable possibility of being related to the study drug will be considered "associated." Events assessed as having no reasonable possibility of being related to study drug will be considered "not associated." In addition, when the investigator has not reported a causality or deemed it not assessable, AbbVie will consider the event associated.

[figure not shown]
If an investigator's opinion of no reasonable possibility of being related to study drug is given, an "Other" cause of event must be provided by the investigator for the serious adverse event.

6.1.4 Adverse Event Collection Period

All serious adverse events as well as protocol-related nonserious adverse events (e.g., infection at liver biopsy site) will be collected from the time the subject signed the study-specific informed consent until study drug administration. From the time of study drug administration until 30 days following discontinuation of study treatment has elapsed, all adverse events will be collected, whether solicited or spontaneously reported by the subject. After 30 days following completion of study treatment and throughout the Post-Treatment Period, all spontaneously reported SAEs will be collected (nonserious AEs will not be collected).

Adverse event information will be collected as shown in [Figure 2](#).

Figure 2. Adverse Event Collection

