| | |
|-------------------|--|
| PegIFN | Pegylated-interferon alfa-2a or alfa-2b |
| PegIFN/RBV | Combination of pegylated-interferon alfa-2a or alfa-2b and ribavirin |
| PI | Protease Inhibitor |
| PIB | Pibrentasvir |
| PK | Pharmacokinetic |
| POR | Proof of receipt |
| PP | Per-protocol |
| PRO | Patient Reported Outcome |
| PR | pegIFN/RBV |
| PT | Post-Treatment |
| QD | Once daily |
| RBC | Red blood cells |
| RBV | Ribavirin |
| RNA | Ribonucleic acid |
| RTV or r | Ritonavir |
| SAE | Serious adverse event |
| SAS | Statistical Analysis System |
| SD | Standard Deviation |
| SF-36v2 | Short Form 36 – Version 2 Health Survey |
| SF-36-MCS | Mental Component Summary |
| SF-36-PCS | Physical Component Summary |
| SOC | System Organ Class/Standard of Care |
| SOF | Sofosbuvir |
| SUSAR | Suspected Unexpected Serious Adverse Reaction |
| SVR | Sustained virologic response |
| SVR ₄ | Sustained virologic response 4 weeks post dosing |
| SVR ₁₂ | Sustained virologic response 12 weeks post dosing |
| SVR ₂₄ | Sustained virologic response 24 weeks post dosing |
| TA MD | Therapeutic Area Medical Director |
| TN | Treatment naïve |
| TSQM | Treatment Satisfaction Questionnaire – Medication |
| ULN | Upper limit of normal |
| V/F | Apparent Volume of distribution |

| | |
|-------|----------------------------------|
| WBC | White blood cells |
| WOCBP | Women of child bearing potential |

Definition of Terms

| | |
|-----------------------|--|
| Study Drug | glecaprevir/pibrentasvir (GLE/PIB) |
| Study Day 1 | First day of study drug dosing |
| Treatment Period | Day 1 through last dose of study drug |
| Post-Treatment Period | Day after the last dose of study drug through Post-Treatment Week 24 or Post-Treatment Discontinuation |

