3.0 Introduction

Hepatitis C virus (HCV) infection is a global health problem, with over 184 million individuals infected worldwide.¹ There are 7 identified HCV genotypes, with genotype 1 (GT1) being the most prevalent worldwide. HCV genotypes 2 (GT2) and 3 (GT3) infections are more common in Latin America (5% to 30%), Europe (20% to 40%) and Asia (30% to 45%).²⁻⁴ HCV GT4 is commonly found in parts of Africa and the Middle East, particularly in Egypt, GT5 is primarily found in South Africa, GT6 is primarily found in south-east Asia, and GT7 has recently been described in Central Africa.⁵

Depending on various risk factors, between 10% and 40% of all patients with chronic HCV infection will develop cirrhosis.⁶ Deaths related to the complications of cirrhosis may occur at an incidence of approximately 4% per year; hepatocellular carcinoma (HCC) occurs in this population at an estimated incidence of 1% to 5% per year.⁶ Patients diagnosed with hepatocellular carcinoma have a 33% probability of death during the first year.⁶ Successful treatment of HCV has been shown to significantly reduce the risk of disease progression and related mortality as well as the development of hepatocellular carcinoma.^{7,8}

At the time of initiation of this study, therapy for HCV had improved considerably with the approval of several interferon (IFN)-free direct-acting antiviral agent (DAA) regimens (ledipasvir [LDV]/sofosbuvir [SOF], SOF, simeprevir [SMV], daclatasvir [DCV], ombitasvir [OBV]/paritaprevir [PTV]/ritonavir [r] + dasabuvir [DSV], elbasvir [ELB]/grazoprevir [GZV], and SOF/velpatasvir [VEL]).^{9,10} However, the approved and recommended regimens are not equally potent across all HCV genotypes and subpopulations. Additional limitations of several current regimens include the requirement of ribavirin (RBV) for certain populations, significant drug to drug interactions, limited options for subjects with renal insufficiency, reduced efficacy in patients with baseline amino acid variants associated with reduced susceptibility to the

HCV nonstructural 5A (NS5A) inhibitors or NS3/NS4A protease inhibitors (PIs), and limited options for patients who have failed IFN-free treatment regimens.

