Child-Pugh Score and Category

All subjects will have Child-Pugh scores assessed. The Child-Pugh score uses five clinical measures of liver disease (3 laboratory parameters and 2 clinical assessments) as shown in [Table 6](#). Child-Pugh score will be determined at the visits indicated in [Appendix C](#) and [Appendix D](#).

Table 6. Child-Pugh Classification of Severity of Cirrhosis

| Parameter | Points Assigned for Observed Findings | | |
|---------------------------------|---------------------------------------|--|------------------------------|
| | 1 | 2 | 3 |
| Total bilirubin, µmol/L (mg/dL) | < 34.2 (< 2) | 34.2 – 51.3 (2 – 3) | > 51.3 (> 3) |
| Serum albumin, g/L (g/dL) | > 35 (> 3.5) | 28 – 35 (2.8 – 3.5) | < 28 (< 2.8) |
| INR | < 1.7 | 1.7 – 2.3 | > 2.3 |
| Ascites* | None | Slight | Moderate to severe |
| Hepatic encephalopathy** | None | Grade 1 or 2 (or suppressed with medication) | Grade 3 or 4 (or refractory) |

Child-Pugh category A: 5 – 6 points; Child-Pugh category B: 7 – 9 points; Child-Pugh category C: 10 – 15 points.

* None.

Slight ascites = Ascites detectable only by ultrasound examination.

Moderate ascites = Ascites manifested by moderate symmetrical distension of the abdomen.

Severe ascites = Large or gross ascites with marked abdominal distension.

** Grade 0: normal consciousness, personality, neurological examination, electroencephalogram.

Grade 1: restless, sleep disturbed, irritable/agitated, tremor, impaired handwriting, 5 cps waves.

Grade 2: lethargic, time-disoriented, inappropriate behavior, asterixis, ataxia, slow triphasic waves.

Grade 3: somnolent, stuporous, place-disoriented, hyperactive reflexes, rigidity, slower waves.

Grade 4: unarousable coma, no personality/behavior, decerebrate, slow 2 to 3 cps delta activity.

Clinical Assessment of Hepatic Decompensation

A clinical assessment of hepatic decompensation, as defined in the Exclusion Criteria, will be performed in all subjects at Study Day 1 prior to dosing, to confirm that the subject has not progressed to hepatic decompensation during Screening.

Hepatocellular Carcinoma Screening Liver Ultrasound

Hepatocellular carcinoma (HCC) screening will be required as a protocol-specified study procedure only at the Screening Study Visit and at the last Post-Treatment Study Visit, as indicated in [Appendix C](#) and [Appendix D](#), for all enrolled subjects. Between those visits, HCC screening should be performed according to standard of care.

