At the Screening Study Visit and at the last Post-Treatment Study Visit, subjects will be required to perform a liver ultrasound to screen for HCC, unless the subject has a historical liver ultrasound (US), CT or MRI performed for HCC screening within 3 months prior to those visits, in which case the result of the historical US, CT or MRI will be used as the result for the Study Visit assessment. A positive ultrasound result suspicious of HCC will be confirmed with CT scan or MRI. Alternate methods of screening for HCC (i.e., MRI or CT) at a study visit should be discussed with the study designated physician.

Patient Reported Outcomes (PRO) Instruments (Questionnaires)

Subjects will complete the self-administered PRO instruments (where allowed per local regulatory guidelines) on the study visits specified in [Appendix C](#) and [Appendix D](#). Subjects should be instructed to follow the instructions provided with each instrument and to provide the best possible response to each item. Site personnel shall not provide interpretation or assistance to subjects other than encouragement to complete the tasks. Subjects who are functionally unable to read any of the instruments may have site personnel read the questionnaires to them. Site personnel should encourage completion of each instrument at all specified visits and should ensure that a response is entered for all items.

Treatment Satisfaction Questionnaire – Medication (TSQM)

Subjects will complete the TSQM questionnaire at the designated study visits listed in [Appendix C](#). The TSQM is a 14-item instrument and includes assessments of satisfaction with a medication's effectiveness (Effectiveness, three items), lack of

side effects (Side Effects; five items), convenience (three items) and the subject's global satisfaction (Global Satisfaction; three items).

The subject should complete the questionnaire before site personnel perform any clinic assessments and before any interaction with the site personnel has occurred to avoid biasing the subject's response. TSQM scores range from 0 – 100 with higher scores indicating better satisfaction. The TSQM should require approximately 5 minutes to complete.

Short Form 36 – Version 2 Health Survey

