- c. If Treatment Extension Criteria has been met, subjects will receive treatment for 12 weeks and will have an additional visit at Week 8 which will include all procedures performed at Week 4.
- d. Subjects need to sign an IRB/IEC approved informed consent for the study (prior to performing any screening or study-specific procedures) and the optional pharmacogenetic sample(s), if applicable.
- e. A complete medical history will be taken at Screening and will be updated at the Study Day 1 Visit.
- f. See specific information regarding adverse event collection in Section 6.1.1.
- g. Height will be measured at the Screening Visit only.
- h. Pregnancy testing is not required for females of non-childbearing potential as defined in the inclusion criteria.

- i. If the IL28B is not collected at Study Day 1, it may be collected at any other visit during the study.
- j. For subjects who have not had a historical qualifying liver biopsy or a historical qualifying FibroScan®.
- k. On Day 1, only FibroTest will be conducted for all subjects. Biopsy and FibroScan will not be conducted on Day 1.
- l. Detail regarding timing of samples is provided in Section **5.3.2.1**.
- m. An HCC Screening assessment is required per protocol in the Screening Study Visit and at the PT Wk 24 or PT D/C Visit. From Day 1 to EOT or premature D/C Study Visit, HCC screening should be performed as part of the Standard of Care for the subject. Please refer to Section **5.3.1.1**, item "Hepatocellular Carcinoma Screening" for details on this study procedure.
- n. PROs should be administered before any study procedures in the order listed in Section **5.3.1.1**. TSQM is not administered at Day 1, only the FSS and SF-36 are collected at Day 1.
- o. TSQM is the only PRO that should be administered at Week 2.
- p. Subjects should bring all study drug to every visit for the site to review adherence. However, the site will record the number of tablets returned only at the Study Drug Accountability Visits at Weeks 4, 8, (Week 12 due to Treatment Extension Criteria) or Premature D/C.

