### **Adverse Events of Special Interest**

For the hepatic decompensation/hepatic failure AE of special interest defined below, the number and percentage of subjects experiencing at least one treatment-emergent AE in the search will be presented overall and by SOC and PT. In addition, a listing of treatment-emergent AEs for subjects meeting the search criterion will be provided. For the hepatocellular carcinoma AE of special interest, a listing of all AEs meeting the search criterion will be provided.

- Hepatic decompensation and hepatic failure
  - Treatment-emergent events only
  - Product MedDRA Query (PMQ) of "Hepatic decompensation and hepatic failure"
- Hepatocellular carcinoma
  - All post-baseline cases, treatment-emergent and non-treatment emergent
  - Search based on specific MedDRA preferred terms of hepatocellular carcinoma, hepatic neoplasm, hepatic cancer, hepatic cancer metastatic, and hepatic cancer recurrent.

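### The one protocol-required HCC scan after baseline falls where only spontaneously reported SAEs are collected, so the SAP's listing of all post-baseline HCC cases may be incomplete

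*Protocol*

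**What the plan says.** **Imaging.** Protocol 5.3.1.1 states that HCC "screening will be required as a protocol-specified study procedure only at the Screening Study Visit and at the last Post-Treatment Study Visit". Appendix C note m fixes the visits: "An HCC Screening assessment is required per protocol in the Screening Study Visit and at the PT Wk 24 or PT D/C Visit". For the interval, 5.3.1.1 adds: "Between those visits, HCC screening should be performed according to standard of care". An ultrasound, CT or MRI from the 3 months before the visit can stand as that visit's result. For a suspicious scan the rule is: "A positive ultrasound result suspicious of HCC will be confirmed with CT scan or MRI". No time limit is given.

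**Collection.** Until 30 days after treatment all AEs are collected, solicited or not. After that, under Protocol 6.1.4, "all spontaneously reported SAEs will be collected (nonserious AEs will not be collected". Appendix D note e repeats this. The PT Period is defined in Protocol 1.3 as "Day after the last dose of study drug through Post-Treatment Week 24 or Post-Treatment Discontinuation".

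**Analysis.** The SAP's section on adverse events of special interest (under 11.2.2) sets the scope of the HCC listing as "All post-baseline cases, treatment-emergent and non-treatment emergent". Its source is a search on five MedDRA preferred terms. The SAP plans no analysis of the HCC imaging results.

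**The concern.** Safety is a primary objective (Protocol 4.1), and HCC is one of two adverse events of special interest in the SAP. The protocol's own scan for it falls in the part of follow-up where collection is narrowest. Three features combine:

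- A lesion found by a scheduled procedure is not clearly a spontaneous report.
- The SAE definitions in 6.1.1.2 do not name malignancy. An asymptomatic lesion that causes no hospital admission becomes an SAE only if the investigator judges it an important medical event.
- The listing is built from AE terms, so a positive scan that was not entered as an AE does not reach it.

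At stake is the completeness of a safety listing. With so few events expected, one unrecorded case would change it materially. No efficacy result, sample size or power figure is involved.

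**Working it through.** The documents state no figure that can be reproduced here. The check is a comparison of texts, followed by arithmetic for scale.

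**Texts side by side**

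1. *Timing.* The required scan is nominally on day 168 after the last dose (24 × 7), and full AE collection stops at day 30. The SAE-only stretch is 168 − 30 = 138 days, or 138/168 = 82% of the PT Period.
2. *Which recording rule applies.* Protocol 6.1 says AEs are recorded whether prompted by a question, noticed by site staff or volunteered. Protocol 6.1.4 and Appendix D note e narrow this after day 30 to spontaneously reported SAEs. A site can cite either text for a lesion seen on the scheduled scan.
3. *Confirmation.* If the ultrasound is done at the Week 24 visit, the PT Period ends at that visit and CT or MRI may follow it. Protocol 6.1 has AEs followed to a conclusion, but that helps only once an AE has been recorded. A suspicious, unconfirmed, nonserious finding after day 30 is not collected under 6.1.4.
4. *Earlier imaging.* Taking 3 months as about 91 days, the earliest scan that can serve for Week 24 is at about day 168 − 91 = 77, still past day 30. This can ease the timing of confirmation but does not lift the SAE-only limit.

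**Scale (illustration only)**

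Inputs:
- N = 330 (Protocol 8.2).
- Follow-up of 56 + 168 = 224 days, assuming every subject completes 8 weeks of treatment and 24 weeks of follow-up.
- Incidence from Protocol 3.0: "hepatocellular carcinoma (HCC) occurs in this population at an estimated incidence of 1% to 5% per year".
- Earlier program, also Protocol 3.0: 6 de novo HCC cases, stated as 0.3%.

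Expected cases = N × annual rate × days/365.25, with a constant rate.

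- Day 1 to PT Week 24: 330 × 224/365.25 = 202.4 person-years. At 1% this gives 2.0 cases, at 5% 10.1.
- After day 30 post-treatment: 330 × 138/365.25 = 124.7 person-years. At 1% this gives 1.2 cases, at 5% 6.2.
- Earlier program's crude proportion: 330 × 0.3% = 1.0 in total. Using 6/2369 = 0.25% gives 0.8, and 6/2265 = 0.26% gives 0.9.

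These are incident cases whose entry into the listing could depend on the SAE route. The documents give no probability that such a case goes unreported, so a number missed cannot be calculated.

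**The case against.** The case on the other side is substantial. Standard-of-care screening continues between the two required scans. Imaging from before the last visit may be used, so confirmation may already exist. SAEs are collected through the whole PT Period, and Appendix D schedules an AE assessment at Week 24. HCC fits the important-medical-event definition readily, and the SAP's term list includes hepatic neoplasm, so a lesion reported before confirmation could still be found. SAP Table 3 runs the Week 24 safety window to day 999, so late data are not cut off at analysis, and SAP 11.2.3 lists all SAEs to the end of the study.

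The 1% to 5% rate may also be high for this trial. Subjects need negative HCC imaging at entry, prior HCC is excluded, and the protocol says successful treatment lowers the risk. The earlier program's rate is not directly transferable either, because most of those subjects had no cirrhosis (1,977 of 2,265 in the safety summary).

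These points rule out stronger readings that a reader might infer:

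- *That the Week 24 scan is the only HCC check after baseline.* It is the only one the protocol requires.
- *That confirmation necessarily falls after collection ends.* No deadline is given, and imaging may predate the visit.
- *That the listing will miss cases, or cannot receive most positive scans.* The SAE route is open, and nothing suggests that most investigators would decline to use it.
- *That hepatic decompensation has the same defect.* Its treatment-emergent limit is an explicit choice. Child-Pugh shift tables cover post-treatment visits (SAP 11.3.1), and serious events appear in the all-SAE listing.

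What the objection leaves standing is the conflict between Protocol 6.1 and 6.1.4, the reliance on judgment about seriousness, the missing rule for capturing a late CT or MRI result, and a listing that does not use the imaging results.

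**Conclusion.** The point holds as a gap in assured completeness. Under the stated rules, an HCC found by the protocol's own scan can remain outside a listing that is meant to hold every post-baseline case. Whether it does so depends on how a site reads the conflicting recording rules and on the investigator's judgment of seriousness.

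The size is small in absolute terms: about 1 incident case in total at the earlier program's crude rate, and about 2 to 10 at the protocol's quoted rate, of which about 1.2 to 6.2 arise after day 30. These figures assume full follow-up, a constant rate and 330 subjects. They are not estimates of missed cases.

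One limit applies. Protocol 6.1.5 and Figure 2 were not in the text available for this point. They may contain further reporting rules, and their absence is not counted against the plan.

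**What to change.** 1. Reconcile Protocol 6.1, 6.1.4 and Appendix D so that suspected or confirmed HCC through PT Week 24 is recorded whatever its seriousness and however it was found.
2. State that, for a suspicious last-visit ultrasound, the subject's record stays open until the CT or MRI result that the protocol already requires has been entered.
3. In SAP 11.2.2, build the HCC listing from the AE terms plus the recorded ultrasound, CT and MRI results.

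The cost is short amendment wording, a field for the imaging result and a wider source for one listing. There are no new visits or scans. The downside is a few extra reports and slightly later closure for subjects with a suspicious last scan.
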